## Procedures

Participants who are eligible for the survey study (Part 1) will be directed to the main survey on REDCap. Survey instruments include: Center for Epidemiological Studies-Depression (CES-D), Yale Food Addiction Scale, Social Phobia Scale (SPS-6), Weight Bias Internalization-Modified (WBIS-M), Perceived Treatment Efficacy, Barriers to Help Seeking Scale (BHSS), Financial Stress Measure, Experience of Racism, Stanford Leisure-Time Activity Categorical Item (L-CAT), as well as individual questionnaire items regarding weight loss history, and effects of COVID-19 on health.

Participants who are eligible for the intervention (Part 2) will be immediately linked to a brief introduction to part 2 of this study at the end of the survey and asked to share their contact information (phone number and email address) if they are interested. Research staff will call participants who are eligible and will review the consent form and answer any questions they have about the study and confirm their interest. The participants will be presented with the full informed consent document and consent to participate via signature provided through a REDCap e-consent. After completing this consent, they will be considered enrolled in the intervention.

Participants who indicate interest in the weight loss program will be informed that they will be sent a second survey in one month. They will be asked if it is ok to use the email address they provide for human subject payment to send them this second survey. This survey will ask them if they have joined a weight loss program in the past month, perceived barriers to joining weight loss programs, and if they are interested in the self-weighing program at that time. If they have not joined a weight loss program

and are interested in the self-weighing program, they will be linked to a brief introduction to part 2 (self-weighing intervention) of this study at the end of the survey and asked to share their contact information. Procedures to consent and enroll them in part 2 will be as described above.

After a participant consents to part 2, they will be sent a standalone questionnaire, called the eating disorder examination questionnaire (EDE-Q). This will be sent to the participant's email address via the REDCap platform.

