## **Intervention**

All intervention elements are delivered remotely. Participants who enroll in the intervention (Part 2) will be mailed a cellular-connected "smart" scale (BodyTrace, Inc). Participants will also receive a study handout with instructions on obtaining an accurate weight (e.g., weigh themselves daily, first thing in the morning, after voiding), suggestions for remembering to self-weigh (e.g., placing the scale in a prominent location), and assistance in interpreting changes in weight (e.g., how to spot trends and noting that day-to-day weight fluctuations are normal). Participants will be informed in the consent process that BodyTrace is a third party and data stored there are not regulated by UF.

Every other week, text messages will be sent to the participant's personal cell phones. Messages will be delivered via REDCap/Twilio integration. Messages will differ based on weight change observed and the frequency of scale use over the preceding 2-4 weeks. A library of messages is provided with this submission.

Participants who regularly self-weigh and are not gaining weight will receive messages encouraging them to continue weighing themselves. A message encouraging use of weight management resources will be sent to participants who gain  $\geq 1.5\%$  of their baseline body weight over a 2 or 4 week period, or if a 3% weight gain from baseline is detected. In particular, the first message sent to those with weight gain will ask if they are willing to receive suggestions for weight management. Participants who respond "yes" will be asked to text back how much time per week are they able to spend managing their weight from the choices of <30 minutes or 30 minutes–2 hours. Participants who select <30 minutes will be given information about a popular, freely available online tool for tracking dietary and physical activity (MyFitnessPal). Participants who select 0.5-2 hours will be asked a few additional questions (e.g., preference for in-person vs remote approaches; barriers to weight

loss), then they will be sent information on selected free/low-cost, evidence-based community-based and commercial weight-loss options.

If participants weigh themselves  $\leq 5$  times per week, we will send them tips to increase self-weighing. If this is followed by a period of very infrequent self-weighing (one time per week or less), they will be sent a message suggesting that they may have gained weight and offering weight management resources.

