#### **3- and 12-month surveys**

- **Weight management behaviors.** At 3- and 12-month assessments, we will ask participants if they have engaged in 19 common strategies for weight management since prior assessment using items from the National Health and Nutrition Examination Survey (NHANES). These strategies include eating less food, eating more or less of certain foods, joining a weight-loss program, or using weight-loss medications. We will also ask: (a) for additional details about some of the strategies used (e.g., which weight-loss program) and (b) about the timing of strategy use. This will tell us whether the messages we sent were related to strategy use. We will also ask about their use of food intake tracking apps.
- **Weight management motivation and readiness.** The same questions from baseline/part 1 survey will be asked.
- **Intervention satisfaction.** At 3- and 12-month surveys, participants will rate specific components of the intervention on a seven-point Likert scale, and will be asked to explain their responses. These components will include: (1) helpfulness of self-weighing instructions provided at study onset, (2) ease-of-use of the scale and reasons for any difficulties, (3) helpfulness of message content, (4) frequency of text messages, (5) overall satisfaction with the program, including the things they did or did not like, (6) likelihood of

recommending the program to others and the reasons why, (7) satisfaction with text messages that offered weight-management resources.

- EDEQ
- CESD
- WBIS-M
- COVID-19 health questions

**Self-weighing data from BodyTrace scale.** Self-weighing frequency and weights from self-weighing throughout the 12 month study will be obtained from BodyTrace via an API.

**Qualitative interviews.** At 12 months, we will conduct interviews with 20 participants to better understand their experience of the intervention. Interviews will be conducted over HIPAA-compliant Zoom, with video if participants are willing and able, or otherwise with audio only. The interviews will cover the survey topics (e.g., message content) in greater depth. See interview guide in myIRB.

**Body weight from EHR.** We will extract all clinical body weight data from the EHR of participants from a period beginning one year prior to the study until 3 years after the study.

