### **Sample size.**

The primary goal of this study is to evaluate feasibility and acceptability of the self-weighing intervention, and the sample size was determined based on standards for achieving that goal. We aim to obtain a sample size of 40 participants for part 2 of this study (intervention). We will cease recruiting for part 1 (survey) when we reach that goal. Thus, we are not able to know our total sample size for the entire study, though we estimate that it will be 200.

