### **Data analyses.**

We will conduct logistic regression analyses to examine predictors of willingness to engage in the weight management interventions, among the variables measured in the survey.

For those who enroll in Part II, we will describe quantitative ratings of intervention satisfaction (mean and standard deviation of satisfaction items) and will conduct qualitative content analyses of the qualitative questions about intervention satisfaction.

To evaluate the potential for intervention effectiveness, we will calculate a sample mean and standard deviation for number of days per week that self-weighing occurs across the 12 month intervention and in each quarter of the intervention (to evaluate sustainability of self-weighing). We will evaluate participants' willingness to learn about weight management resources offered by the research team, initiation of use of resources, and sustain use of resources among those participants offered resources. Finally, we will characterize weight change by reporting means, standard deviations, and the portion who gain  $\geq 3\%$  of baseline weight in order to inform planning for our subsequent trial.

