Data obtained during video- or audio-recorded interviews may be used in future publications but will not be linked with names or identifying information. The audio file will be downloaded from Zoom, saved on a password protected computer in our University office, and transcribed for responses to the questions. No names will be included on the typed files. If any personal information comes up during the interview, the information will be redacted from the transcript. Quotes from the interview may be used in future publications, but will not be linked with names or identifying information. All audio recordings will be deleted from the network drive where it will be stored, with assistance from the IT department once they have been de-identified and transcribed, no later than 12 months after they are recorded.

Another area of risk for this study is the potential for patients to engage in unhealthy or risky health behaviors while pursuing weight loss. Because this study does not provide close supervision by trained professionals and patients may encounter suggestions from the support network that are not consistent with guidelines. This risk is not dissimilar, and is likely lesser, from what individuals encounter when they

attempt weight loss on their own, which over 50% of adults with obesity report attempting in a given year.

Further, it is generally unsafe for women who are pregnant to engage in weight loss efforts, and it is an exclusion criteria in our study. As such, participants will be withdrawn from the study if they become pregnant.

Some participants may find self-weighing to be aversive. However, those participants will have the chance to decline enrolling in the intervention or to withdrawal from the intervention. Although it is possible that regular self-weighing may be aversive to some individuals who enroll, past research clearly demonstrates that there is no increase in eating disorder symptomatology among individuals assigned to daily self-weighing.

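### Sustained self-weighing is judged only from separate quarterly means and SDs; a within-person change with a 95% CI, on a fixed denominator and start date, would answer the question better at almost no cost

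*Combined protocol and SAP*

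**What the plan says.** All of this is in the combined protocol and SAP.

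- **Data analyses.** As part of assessing potential effectiveness, "we will calculate a sample mean and standard deviation for number of days per week that self-weighing occurs across the 12 month intervention", and the same summary is made "in each quarter of the intervention (to evaluate sustainability of self-weighing". No within-person change, confidence interval, longitudinal model or criterion for calling weighing sustained is given. Nor is there a denominator for each quarter, or a rule on whether days without a transmitted weight count as zero or missing.
- **Body of data.** Under the assessments, "Self-weighing frequency and weights from self-weighing throughout the 12 month study will be obtained from BodyTrace via an API". Person-level records will therefore exist for the whole period.
- **Procedures.** Of the e-consent: "After completing this consent, they will be considered enrolled in the intervention".
- **Intervention.** "Participants who enroll in the intervention (Part 2) will be mailed a cellular-connected" scale. No shipping time is given, and no section defines day 0 of the 12 months.
- **Section 6 (Possible Discomforts and Risks).** "participants will be withdrawn from the study if they become pregnant". Those who find weighing aversive may also leave the intervention. No dropout rate is given and no rule for the later data of people who leave.
- **Sample size.** "We aim to obtain a sample size of 40 participants for part 2 of this study (intervention"). No SD, correlation, power or precision target is stated.

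**The concern.** Sustainability is a question about the same people over time: do those who weigh often at the start still do so at the end? Separate quarterly summaries describe the group at four points. They give neither the uncertainty of the change nor its spread between people, and both are useful for designing the larger trial that this pilot is meant to prepare.

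Two open definitions add to this. If people who leave are taken out of later quarters, and if they were low weighers, the later means rise for reasons unrelated to persistence. If quarter 1 is counted from consent, it contains days before a study scale was available, which lowers its mean. Either choice would make a fall from quarter 1 to quarter 4 look smaller. At stake is part of the evidence for Aim 3, which asks whether the intervention can promote regular self-weighing.

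**Working it through.** The plan has no figure of its own to reproduce. The only input from the documents is n=40. All SDs, correlations, leaver shares, weighing rates and delays below are assumptions for illustration.

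**1. Precision of the change.** With the same SD in both quarters and within-person correlation r, the 95% half-width is

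- quarters treated as independent: 1.96 × SD × √(2/n)
- paired: 1.96 × SD × √(2(1−r)/n), which is the first value times √(1−r).

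For SD 2.2 and n=40: 1.96 × 2.2 × √(2/40) = 0.96. Multiplying by √0.7, √0.5 and √0.3 gives 0.81, 0.68 and 0.53. Over a range of SDs (days/week):

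| SD | independent | r=0.3 | r=0.5 | r=0.7 |
|---|---|---|---|---|
| 1.5 | 0.66 | 0.55 | 0.46 | 0.36 |
| 2.0 | 0.88 | 0.73 | 0.62 | 0.48 |
| 2.2 | 0.96 | 0.81 | 0.68 | 0.53 |
| 2.5 | 1.10 | 0.92 | 0.77 | 0.60 |

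The variance is smaller by a factor 1/(1−r), that is 1.4 to 3.3 for r from 0.3 to 0.7.

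**2. What pairing does not change.** If the same 40 people are in both quarters, mean(Q4) − mean(Q1) equals mean(Q4 − Q1) exactly. The point estimate is the same; only its precision is lost.

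**3. Who is counted.** Let a share p leave after quarter 1, having weighed L days/week in it. Those who stay go from 5.2 to 4.7. Then Q1 = pL + (1−p) × 5.2. Q4 is 4.70 among those still present, or (1−p) × 4.7 if all enrolled are kept with zero days after leaving.

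| p, L | Q1 | Q4, those present (change) | Q4, all enrolled (change) |
|---|---|---|---|
| 20%, 2.5 | 4.66 | 4.70 (+0.04) | 3.76 (−0.90) |
| 10%, 2.5 | 4.93 | 4.70 (−0.23) | 4.23 (−0.70) |
| 20%, 5.2 | 5.20 | 4.70 (−0.50) | 3.76 (−1.44) |

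In the first row, the −0.90 is made up of 0.8 × (−0.5) = −0.40 from decline among those who stay and 0.2 × (−2.5) = −0.50 from scoring leavers as zero. A paired change among those who stay would be −0.50 in every row. In the third row, where leavers weigh as often as the others, dropping them gives that same −0.50.

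**4. When quarter 1 starts.** If a 91-day quarter 1 began at consent and the scale arrived d days later, a true rate of 5.0 days/week would be recorded as 5.0 × (91−d)/91. For d = 7, 14 and 21 this is 4.62, 4.23 and 3.85. A 14-day lag would offset a true fall of 5.00 − 4.23 = 0.77.

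**The case against.** A reader might infer that the plan is biased toward finding weighing sustained. The documents do not support that, for these reasons.

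- **Pairing.** Step 2 shows that dropping it cannot hide a mean decline when the denominator is fixed. The plan also proposes no unpaired interval, so 0.96 is what its summaries would allow, not an analysis it has chosen.
- **Start date.** A reader might take quarter 1 to begin before the scale arrives. The Procedures section says when a person is enrolled, not when the 12-month clock starts. Quarters of the intervention could equally run from receipt of the scale. Even if counted from consent, only quarter 1 is depressed: a fall from quarter 2 to quarter 4 stays visible, and the 12-month mean errs against the intervention.
- **Denominator.** Nothing says that leavers will be dropped, and a sample mean may well cover all 40. Scale data arrive passively, so a person who merely stops weighing can be counted as zero. No dropout rate is given, and nothing shows that leavers weigh less.
- **Weight of the result.** This is a single-arm pilot whose primary goal is feasibility and acceptability. Self-weighing stands beside resource use and weight change as signs of potential, with no success threshold tied to the quarterly means. Person-level data are kept, so a paired change can be computed later.

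All of this stands, and it limits the point to a better method and three missing definitions. It does not remove the point. A descriptive estimate still needs a defined population and time zero, and step 3 shows that the rule for leavers can decide how the result reads. It is better fixed before the data are seen.

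**Conclusion.** The point holds as an improvement of modest weight. The planned quarterly means and SDs cannot give the precision of the within-person change, while the data to do so are already being collected. Under the assumed SD of 2.2 and n=40, pairing takes the 95% half-width from 0.96 to between 0.81 and 0.53 days/week for correlations of 0.3 to 0.7. That gain assumes equal SDs in the two quarters and a positive correlation. Scoring leavers as zero would tend to raise the quarter 4 SD and lower the correlation, so the actual gain may be smaller.

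The denominator after withdrawal and the start of quarter 1 are undefined, not wrongly defined. A masked decline is possible under particular choices and particular leaver behaviour; it is not what the plan states. The figures in steps 3 and 4 show how far those choices could matter and do not predict what will happen.

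**What to change.** In the Data analyses section:

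- Make the sustainability result the within-person change in days per week from quarter 1 to quarter 4 with a 95% CI, from paired differences or a mixed model over the four quarters. Keep the quarterly means and SDs as description. No hypothesis test is needed.
- Keep all enrolled participants in the denominator of every quarter. In the main analysis, count zero days after voluntary withdrawal; in a sensitivity analysis, treat those days as missing. State separately how days after withdrawal for pregnancy are handled, since that exit is not a choice to stop weighing.
- Report the number contributing to each quarter.
- Count quarter 1 from scale delivery, so that days without a scale are left out but people who never start weighing are kept.

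The cost is a few lines of text and a delivery date logged for each participant, which has to be captured as the study runs. The downside is that later-quarter means may look less favourable than under a looser rule. Nothing in the delivery of the intervention or its text messages needs to change.

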### **Assessments and measures.**

All assessments will be conducted remotely via REDCap. In addition to the Part 1 survey, and the one-month follow-up Part 1 survey (for those who qualify), participants who enroll in the intervention will complete survey assessments at 3 and 12 months, and a portion of participants will be invited to a qualitative interview at 12 months.

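### Weight change is to be reported to plan the next trial, but neither follow-up survey collects a weight, so anyone without a scale or clinic weight near month 12 drops out of that result

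*Combined protocol and SAP*

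**What the plan says.** The Data analyses section ends with a weight result: "we will characterize weight change by reporting means, standard deviations, and the portion who gain" at least 3% "of baseline weight in order to inform planning for our subsequent trial". It does not name the source of the weights, which weight is the baseline, the time point or window, or how people without a weight are counted.

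Under Assessments and measures, "participants who enroll in the intervention will complete survey assessments at 3 and 12 months", and "All assessments will be conducted remotely via REDCap". The listed survey content is weight management behaviors, motivation and readiness, satisfaction, the EDE-Q, CES-D and WBIS-M, and COVID-19 questions. No measured or self-reported weight is listed. The note that Part 1 questions are repeated is attached to motivation and readiness only. Self-reported weight and BMI appear only in the Part 1 eligibility criteria.

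Two passive sources supply follow-up weights. One is the home scale, whose readings come through the BodyTrace interface. The other is clinical care: "We will extract all clinical body weight data from the EHR of participants", from one year before the study to three years after it. The Abstract presents EHR weight as the intended source, and Aim 2 makes the adequacy of those weights a feasibility outcome.

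**The concern.** Each source depends on something the plan does not control. A scale reading needs continued self-weighing, and the plan treats this as uncertain by describing frequency quarter by quarter to judge whether it is sustained. An EHR weight needs a clinical contact at which the patient is weighed. A participant who has stopped weighing and has no clinical weight near month 12 contributes nothing to the weight result, even after completing the 12-month survey.

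At stake is a planning figure. If those without a weight differ from the rest, the mean change and the share gaining at least 3% describe a subgroup and not the enrolled sample. A month-12 weight that was never collected cannot be recovered later.

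**Working it through.** **Plan's own figure.** There is none to reproduce. The Sample size section gives 40 participants for Part 2 and says "the sample size was determined based on standards for achieving that goal", with no expected rate, standard deviation or precision target.

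**Inputs.** N = 40 comes from the Sample size section. Everything else is assumed: an observed share gaining at least 3% of 25%, and a proportion without a month-12 weight (m) of 10% to 40%.

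**Step 1: bounds that need no assumption about direction.** With x gainers among the observed and k people without a weight, the share in all 40 lies between x/40 (no missing person gained) and (x + k)/40 (all did).

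| m | Observed | x | k | Lower bound | Upper bound |
|---|---|---|---|---|---|
| 10% | 36 | 9 | 4 | 9/40 = 22.5% | 13/40 = 32.5% |
| 20% | 32 | 8 | 8 | 8/40 = 20% | 16/40 = 40% |
| 30% | 28 | 7 | 12 | 7/40 = 17.5% | 19/40 = 47.5% |
| 40% | 24 | 6 | 16 | 6/40 = 15% | 22/40 = 55% |

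For scale, complete data with 10/40 = 25% would give a Wilson 95% interval of 14.2% to 40.2%. That interval expresses sampling error about a wider population. The bounds express what is unknown about the 40 themselves, and they come on top of it.

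**Step 2: direction.** Reported share minus share in all enrolled = −m × (share gaining among the missing − share gaining among the observed). With m = 20% and 25% observed:

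- 50% among the missing: −0.20 × (0.50 − 0.25) = −5 points (reported share too low).
- 35% among the missing: −0.20 × (0.35 − 0.25) = −2 points.
- 15% among the missing: −0.20 × (0.15 − 0.25) = +2 points (reported share too high).

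The sign turns entirely on a quantity the documents do not give.

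**Step 3: mixing sources.** A home-scale baseline compared with a clinic follow-up weight can shift the result without any missing data. Assume weight change is normal with mean 0 and SD 5% of body weight, and that clinic weights read 1% heavier. The share at or above 3% then moves from 1 − Φ(3/5) = 27.4% to 1 − Φ((3 − 1)/5) = 34.5%. This is why the baseline and follow-up sources need to be named.

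**The case against.** The strongest reply is that passive weight capture is the design under test. The Abstract assigns the surveys to feasibility and acceptability and takes weight from the EHR, in preparation for a pragmatic trial. Obtaining EHR weights is a feasibility outcome. The EHR is also not a weak source on its face: recruitment draws on patients with a BMI recorded, or a primary care appointment, in the past month, and eligibility requires an EHR weight in the prior year. Its completeness does not depend on scale use, so a person is lost only when both sources fail. All of this stands, and any fix must leave the EHR test intact. It does not supply a weight for those whom both sources miss, or a rule for counting them.

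A reader might infer that the share gaining at least 3% will be understated, because very infrequent weighers are to be told this: "they will be sent a message suggesting that they may have gained weight and offering weight management resources". The documents do not support that step. The text is an intervention message saying that gain is possible. It is neither evidence about outcomes nor a missing-data assumption, and it says nothing about who lacks an EHR weight. Clinic attendance could move the share either way.

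A third objection concerns the remedy. A scale prompt at month 3 could restart weighing on later days and so alter the Aim 3 frequency outcome, and dropping only the prompted day would not undo that. This also stands, and it rules out a month-3 scale prompt.

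**Conclusion.** The point holds as a gap in collection and reporting. The plan promises a weight result for trial planning, schedules no weight to support it, and gives no source, window or rule for people without a weight. How many of the 40 this affects cannot be known from the documents. With an assumed 25% observed share, 20% missing leaves the figure for all 40 anywhere from 20% to 40%. Selective loss of non-weighers is plausible, but a claim that gain will be understated goes beyond the documents.

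Priority is minor. The outcome is descriptive, no test or decision rule depends on it, and the study's primary goal is feasibility and acceptability.

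**What to change.** **Assessments and measures**

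- Add a self-reported current weight item to the 3- and 12-month surveys.
- With the 12-month survey, request one reading on the study scale, taken after the 12-month self-weighing frequency window has closed so that Aim 3 is unaffected.
- Add no scale prompt at month 3.

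**Data analyses**

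- Keep the obtaining of EHR weights as its own feasibility outcome, judged without the added weights.
- Name the source of the baseline weight and of the 12-month weight.
- Where no other 12-month weight exists, use the requested scale reading, with self-report as the fallback.
- Report how many of the 40 have a weight from each source.
- Show the share gaining at least 3% twice, with missing people counted as gained and as not gained.

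**Cost.** One extra item in each of two existing paid surveys, one requested weigh-in on a scale already mailed to participants, and scale data retrieval that runs slightly past month 12. Self-report brings some measurement error. Neither addition reaches people who do not answer the survey, so the two-way count is still needed.
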